2.2 Objectives

To collect data from patients attending the UK specialist Asthma centres:

To provide a description of the factor structure of the SAQ and to demonstrate equivalence across populations.

To show that the SAQ correlates in an acceptable manner with the Mini Asthma Quality of Life Questionnaire (MiniAQLQ) and EQ-5D-5L (EQ5D)

To show that the SAQ is a discriminator of patients who have different frequencies of exacerbations and different levels of prednisolone consumption.

To show that the SAQ is equivalent in discrimination for exacerbations to the MiniAQLQ or EQ5D but is a better discriminator than these questionnaires for treatment levels of oral corticosteroids.

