2.6.3 Sample size calculation

Sample size determination is based on the analysis where the greatest number of patients is needed, namely factor analysis. For exploratory factor analysis the number of participants needed per item varies but ranges between 15 and 20 participants per item [18, 19]. There are 16 items in the SAQ. Thus, data from 240 – 320 participants is needed for any factor analysis, (80 – 107 participants from each centre.)

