2.7 Data Collection Method

After providing written informed consent, participants will be provided with a pack consisting of a consent form, and the following questionnaires: (a) SAQ, (b) MiniAQLQ, and (c) EQ-5-5L (d) ACT/ACQ.

All clinic data will be input onto the Baseline Case Report Form (CRF) (Appendix 9) by a research nurse. This data and the completed pseudonymised questionnaires will be emailed to the Plymouth RA (JL) via NHS email. This data will utilise a participant number system. Each site will place a copy of the completed questionnaires into the patient's notes as they may contain relevant clinical information for current and future treatment.

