2.8 Analysis

Factor analysis of the SAQ A trial principal axis factor analysis with scree plot will be calculated. On the basis of factor loadings on the first factor, it will be decided whether it is legitimate to provide an overall score for the questionnaire. Using the scree plot to determine factor number, an oblique rotation will be carried out and interpretation of emerging factor loadings (from the pattern matrix) determined.

Correlations between questionnaires

Correlations between questionnaires will be calculated using Pearson Correlations.

Discriminant validity We will test for significant differences between the SAQ and other scales using a mixed design analysis of variance (one within and one between) where groups are defined in two ways (a) maintenance dose oral corticosteroids and (b) cumulative dose oral corticosteroids. The aim of this analysis is to investigate whether the SAQ has better discriminant validity than other scales. First the interaction term of the analysis of variance will be used to determine whether sensitivity differs across all groups. Second, because the SAQ is expected to be more sensitive to discrimination at the top end of prednisolone use, a mixed design analysis of variance will be conducted on the two highest doses of prednisolone only.

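### Section 2.8 tests a directional claim about the SAQ with an omnibus scale-by-group interaction, which has no sign and, with three or more scales, is not specific to the SAQ

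*Protocol*

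**What the plan says.** Protocol section 2.2 sets a directional objective that names the SAQ: for OCS, the SAQ "is a better discriminator than these questionnaires for treatment levels of oral corticosteroids", the questionnaires being the MiniAQLQ and the EQ5D. Section 2.8 (Discriminant validity) repeats it: "The aim of this analysis is to investigate whether the SAQ has better discriminant validity than other scales".

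The method in 2.8 compares the SAQ with the other scales "using a mixed design analysis of variance (one within and one between"), with groups formed by maintenance dose and by cumulative dose of OCS. Two steps follow:

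- Step 1: "First the interaction term of the analysis of variance will be used to determine whether sensitivity differs across all groups".
- Step 2, because the SAQ is expected to do better at the high end of prednisolone use: "a mixed design analysis of variance will be conducted on the two highest doses of prednisolone only".

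Neither step names a SAQ-versus-comparator contrast, a direction, or a rule for concluding that the SAQ is better. Section 2.8 does not say how many scales enter one ANOVA. The pack in section 2.7 holds "a) SAQ, (b) MiniAQLQ, and (c) EQ-5-5L (d) ACT/ACQ".

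**The concern.** A scale-by-group interaction asks whether any scale's profile over the dose groups differs from any other's. The objective asks whether one named scale has a steeper profile than each of two others. These are different questions, and putting every scale on a common metric does not bring them together.

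A significant interaction could arise because the SAQ is the least sensitive scale, or because the MiniAQLQ and EQ-5D-5L differ from each other while the SAQ matches the better one. This is the protocol's test of the main advantage claimed for the SAQ, its sensitivity to OCS burden. A significant result on the stated criterion would not by itself support that claim.

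**Working it through.** **The plan's own figure.** The part 1 sample size comes from factor analysis: "ranges between 15 and 20 participants per item", with 16 items. 15 × 16 = 240 and 20 × 16 = 320; over three centres, 3 × 80 = 240 and 3 × 107 = 321. This reproduces "Thus, data from 240 – 320 participants is needed for any factor analysis, (80 – 107 participants from each centre"). The protocol gives no power for the interaction test.

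**Inputs.** From the protocol: N = 240 to 320; one within factor (scale) and one between factor (OCS group). Assumed, because the protocol gives none of them: s = 3 scales, each with SD 1 and oriented the same way; g = 4 equal groups (n = 60 or 80); correlation between scales ρ = 0.7; 5% level; gaps in SD from lowest to highest group.

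**Formula.** For the interaction, df1 = (g − 1)(s − 1) = 6, df2 = (N − g)(s − 1) = 472 at N = 240, and λ = n Σ(interaction effect)² / (1 − ρ), with power from the noncentral F.

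**Step 1, one scale differing by 0.3 SD, linear over dose.** The centred differences are d = (−0.15, −0.05, 0.05, 0.15), so Σd² = 0.05. When one scale of three differs, the interaction effects are ±2/3 d for that scale and ∓1/3 d for each of the others, so the sum of squares is (4/9 + 1/9 + 1/9) Σd² = 2/3 × 0.05. Hence λ = 60 × 0.05 × (2/3) / 0.3 = 6.67. The sign of d, and which scale differs, drop out:

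| Truth (SAQ / MiniAQLQ / EQ-5D-5L, SD) | λ at N = 240 | Significant, N = 240 | N = 320 |
|---|---|---|---|
| SAQ better (0.6 / 0.3 / 0.3) | 6.67 | 44% | 58% |
| SAQ worse (0.3 / 0.6 / 0.6) | 6.67 | 44% | 58% |
| SAQ tied with MiniAQLQ (0.6 / 0.6 / 0.3) | 6.67 | 44% | 58% |

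With groups split 50/20/20/10%, all three rows become 39% and 51%. When all scales have equal gradients, simulation gives 5.1% and 4.5%. The test therefore has the right size for its own null hypothesis, but that null is not the study's question.

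**Larger gaps.** If the SAQ and MiniAQLQ both show 0.5 SD and the EQ-5D-5L is flat, the interaction is significant in 92% (N = 240) and 98% (N = 320). Over 3 to 5 groups, 3 to 4 scales and ρ from 0.5 to 0.8, the N = 240 figure runs from 56% to over 99%. If the SAQ is worse by 0.4 SD, the rates are 72% and 86%.

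**Step 2, two groups, three scales, 0.3 SD.** Σd² = 2 × 0.15² = 0.045 and λ = 60 × 0.045 × (2/3) / 0.3 = 6.0 on 2 and 236 df. This gives 58% (71% at N = 320), again the same whether the SAQ is better, worse, or tied with one scale while the other is weaker.

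**A signed contrast.** SAQ minus one comparator has variance 2(1 − ρ) = 0.6. When the two scales tie, a two-sided 5% contrast favours the SAQ in 2.5% of studies.

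**Power of the alternatives, N = 240.**

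- Linear advantage, trend contrast against one comparator: noncentrality √(60 × 0.05 / 0.6) = 2.24, power 61%, against 44% for the omnibus.
- Linear advantage, trend contrasts against both comparators jointly: 44% (simulated), the same as the omnibus. With four scales, joint power over the three comparators is 36% against 42%.
- Advantage of 0.3 SD in the top group only: Σd² = 0.09 × 0.75 = 0.0675, so λ = 60 × 0.0675 × (2/3) / 0.3 = 9.0 and omnibus power is 58%. The linear trend against one comparator has noncentrality 0.45 / √(0.6 × 5 / 60) = 2.01 and power 52%. A top-versus-rest contrast has √(60 × 0.0675 / 0.6) = 2.60 and power 73%.
- Top-group-only advantage with other splits, linear trend against omnibus: 38% v 41% (50/20/15/15%) and 22% v 29% (50/20/20/10%).

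**The case against.** **Section 2.8 does not say that significance means the SAQ is better.** It says the interaction shows whether sensitivity differs, which is what an interaction does, and group means would show direction. A reader might infer that the protocol would declare the SAQ superior even if it came out worst. The text does not support that. What stands is narrower: the stated aim is better discrimination, the only criterion fixed is the interaction, and no step leads from one to the other. Inspecting means is not a test of the SAQ against each comparator.

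**Pairwise ANOVAs may be meant.** The wording can be read as the SAQ against each other scale in turn. That would restore specificity, and the tied scenario would no longer apply. The F test would still be unsigned. In step 2, a pairwise ANOVA on two groups is exactly a two-sided one-df contrast, so no power is lost there; only the direction needs stating.

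**The omnibus test wastes power.** A reader might infer this too, and it does not hold in general. A linear trend gains only if the advantage is linear and only for each comparator taken separately. For the top-end advantage that 2.8 itself expects, it loses to the omnibus in all three group splits above.

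**This belongs in the SAP.** Dose cut-points and follow-up contrasts often do. Here, though, the protocol has itself chosen the decision statistic, and that choice does not match its objective.

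**Conclusion.** The concern holds as a point of validity. The criterion in 2.8 cannot distinguish a better SAQ from a worse one and, with three or more scales in one ANOVA, cannot tie the result to the SAQ at all. Both properties follow from the test itself and need no assumed values.

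The size does rest on assumptions. With three standardised scales, four groups, ρ = 0.7 and a 0.3 SD gap, the interaction is significant in about 39–44% of studies at N = 240 and 51–58% at N = 320, whichever of the three situations is true.

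The flaw affects the inference in 2.8, not the part 1 sample size. It should be corrected before analysis.

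**What to change.** In section 2.8, base the conclusion that the SAQ is better on two pre-specified signed contrasts across OCS groups: SAQ minus MiniAQLQ and SAQ minus EQ-5D-5L, on standardised scores oriented the same way. Report each with a 95% confidence interval. Claim superiority over a comparator only if its interval lies wholly on the side favouring the SAQ.

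Match each contrast to its hypothesis: a trend or other ordered contrast for the all-groups step, and a pre-specified top-group contrast for step 2. Avoid SAQ minus the mean of the others as the decision contrast. In the scenario with both SAQ and MiniAQLQ at 0.5 SD and a flat EQ-5D-5L, it favoured the SAQ in 58% of simulated studies at N = 240 although the SAQ only tied the best scale. State which scales enter each analysis, and keep the omnibus interaction and group means as description.

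The cost is wording in the protocol and SAP, with no new data. The downside is that a chosen contrast loses power if the true dose pattern differs from it, including a monotone gain confined to the top group when a linear trend is used.

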3.0 Sensitivity to Change Study

3.1 Aim

To assess the sensitivity to change of the SAQ, for patients who initiate a new biologic treatment for their asthma.

To determine the SAQ's minimal clinically important difference (MCID).

3.2 Study Design

Type of study: A multi-centre sensitivity to change study, using the SAQ, other questionnaire measures and clinic data

Duration of the study: 18 months.

Sample size: Between 30 and 50 participants per each of the five participating sites:

1. University Hospitals Plymouth, NHS Foundation Trust, Plymouth, UK
2. Royal Brompton and Harefield NHS Foundation Trust, London, UK
3. University Hospital of South Manchester, Manchester University NHS Foundation Trust, UK
4. Birmingham Heartlands Hospital NHS Foundation Trust, Birmingham, UK
5. Royal Devon and Exeter Hospital NHS Foundation Trust, Exeter, UK

Baseline questionnaire data from participants recruited for this part of the study will be added to the dataset for part 1.

3.3 Study outcome measures

3.3.1 Investigation questionnaires:

1. Severe Asthma Questionnaire (SAQ) (Appendix 2)
2. Global Rating of Change Questionnaire (Appendix 10)

This scale will be used by participants to indicate how much better they feel since commencing a biologic treatment for asthma. The 11-point scale ranges from -5 (a great deal worse) to 5 (A great deal better) [20].
3. EQ-5D-5L (Appendix 3)

3.3.2 Clinic Data to be collected:

Baseline characteristics:

Age

Sex

Spirometry: absolute FEV1 (litres) and percentage of predicted FEV1 (FEV1 %)

Forced Vital Capacity (FVC) (litres)

Body Mass Index (BMI)

Asthma severity: Treatment level by drug class classified by GINA step
Maintenance OCS dose (mg/day)Health care utilisation:
Emergency Department attendance in the last 12 months
Hospital admissions in the last 12 months

Clinic Data Outcome Measures to be recorded at each treatment visit:

Weight (Kg)
Maintenance OCS dose (mg/day)
Number of exacerbations since last clinic visit requiring OCS Health care utilisation, the number of:
Emergency Department attendances since last clinic visit
Hospital admissions since last clinic visit.

Must be recorded on the follow-up CRF at the final study visit (16 weeks), (weeks 4, 8 and 12 are optional):

FEV1 (litres)
FEV1 (% predicted)

3.4 Recruitment and Consent

Patients will be identified as eligible to participate by a health professional familiar with them. When possible, these patients will be contacted by a health professional two weeks before they are due to attend for their asthma treatment, and invited to participate. This contact will be made by posting a Patient Invitation Letter (Appendix 11) and Patient Information Leaflet with a consent form (Appendix 12) out to the patient.

The Invitation Letter and Patient Information Leaflet will include instructions to read the material carefully. Contact details for the centres PI, and researcher will be included on the Patient Information Leaflet, and can be contacted if the patient has questions. If they wish to participate after reading this information, patients may complete the consent form and bring it with them to their next asthma clinic appointment.

Alternatively, when attending their appointment, patients who have been identified as eligible to participate in this study, will be asked if they are interested in participating. If so, a health professional will brief and consent the patient or alternatively, will introduce the patient to a researcher who will facilitate this. The participant will be provided with a Patient Information Leaflet. The patient will be assigned a participant number at this time.

The researcher will be available to answer detailed question about the research project. In addition, as this is a clinic setting, multiple health professionals will also be present, who will be aware of this project, and be able to answer questions, or refer the patient to the researcher if necessary. Patients will have all questions answered, before they sign a consent form, and will be aware that they can withdraw at any time if they choose.

3.4.1 Inclusion Criteria

Patients commencing a biologic treatment for their severe asthma (GINA step 4 & 5), as per NICE guidelines

3.4.2 Exclusion Criteria

Patients will be excluded from the study if they are unwilling to participate

In the opinion of the physician responsible for the care of the patient, the patient has a condition, other than asthma which is significantly contributing to their respiratory symptoms, e.g. lung cancer, heart failure or severe COPD.

3.4.3 Sample size calculation

Three types of analysis are planned. Sample size is based on analysis 2 (see below where the sample is divided into quartiles and we test whether there are significant differences between quartiles. Four groups of 25 patients will detect an effect size of 0.3 with a power of 70% at a significance level 5%. The total sample is therefore 100 participants. The addition of a fifth site with the aim of also recruiting 25 patients will mean this analysis remains sufficiently powered even if one of the other sites under-recruits.

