3.6 Analysis

The SAQ provides two scores, the SAQ score which is the mean of all 16 domain specific items, and the SAQ-global score which is a single item score based on the SAQ-Global, which itself is based on a Borg scale [21]. Borg scales use multiple quantifiers at empirically derived points along the scale with the aim of achieving a ratio scale. In this analysis plan, the term SAQ will refer to both the SAQ score and the SAQ global score. Separate analyses will be carried out on the SAQ score and SAQ-global. Several analyses will be carried to ensure that the MCID concept is fit for purpose.

Data from 4, 8, 12 and 16 weeks will be compared to the data collected at week 0 (baseline), providing 4 change scores per patient. Patients can indicate any one of 5 levels of improvement in any of the four weeks, or, if there is no change or deterioration, up to 11 types of change. If patients report the same level of global rating of change at each of the four time points (e.g., they record 'a little better' at week 4 and 'a little better at week 8), the average SAQ change score will be calculated for that patient. This average will then be used as the SAQ change for that particular level of global rating of change. This procedure is followed so that each patient can contribute just one value to the population average of the SAQ change score at any level of global change, and which, in the case of the level of 'a little better' is used to calculate the MCID. We shall carry out three analyses to check on the validity of the MCID concept. If the checks come out positive, then the existing method of calculating the MCID (i.e., as the change in the SAQ that maps on to the global rating of change criterion of 'a little better) will be adopted.

If the checks are negative – i.e., suggesting some revision to the way the MCID concept is employed – then we will adapt the methodology in accordance with our findings.

What degree of change on the SAQ is associated with each of the 5 levels of improvement and 5 levels of deterioration on the global rating of change score?

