The mean, confidence intervals, and standard deviation of change of the SAQ will be calculated for each level of change in the GRCQ. These means will then be plotted (change in SAQ on x axis, global change on y axis) to show the relationship between change and perceived change at different degrees of change. These results should show that the change in the SAQ increases with increase in global change scores, and will be tested for by analysis of variance. This analysis is needed to show that the MCID is specific to the level of change of 'a little better' or 'a little worse' rather than any other level of global rating of change. The analysis will also check whether 'a little better' is equivalent in terms of 'a little worse' in terms of SAQ change.

Is the MCID transitive – i.e., is the MCID independent of level of deficit of quality of life?

Patients will be allocated to quartiles based on severity of the SAQ score at week 0. The mean, confidence intervals and standard deviation of change scores for change at 'a little better' will be calculated. Analysis of variance will be calculated for the four quartiles to test of transitivity. Effect size (eta) will be calculated. This analysis is needed to show that the MCID level can be applied across the full range of deficit of quality of life.

Are items in the SAQ equivalent with regard to the MCID – i.e., is change in all the 16 SAQ items equivalent in terms of their relationship with the global rating of change?

To test for equivalence, change in each of the 16 items of the SAQ and the SAQ-global will be correlated against the global rating of change score. These correlations will be examined and interpreted. Regression will be explored, but may be ruled out due to co-linearity. This analysis is needed to show whether weighting of items is needed when calculating the MCID, or whether the MCID is based simply on the mean of all items.

Demographic information analyses

In addition, we will also test whether baseline characteristics are similar across the four quartile groups and investigate whether the change in SAQ is related to the collected demographic and clinical data.

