If the above show no problems with the existing methodology, then the MCID will be calculated from the average SAQ change for the rating of 'a little better'. That is, any patient who has provided a global rating of change of 'little better' will contribute an initial and final SAQ score to produce a SAQ difference score for each patient, and the average of the SAQ difference scores across patients will be then form the MCID. If there are problems, then we shall modify the MCID, for example, having different values for different levels of quality of life deficit (see 2 above) or by using a weighting of items (see 3 above).

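### The 70% power in section 3.4.3 counts all 100 recruits, but the test it refers to uses only patients who rate themselves *a little better* at least once

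*Protocol*

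**What the plan says.** Section 3.4.3 bases the sample size on the second of three planned analyses, the comparison of quartiles: "Four groups of 25 patients will detect an effect size of 0.3 with a power of 70% at a significance level 5" per cent. It goes straight on to "The total sample is therefore 100 participants". A fifth site, aiming for another 25 patients, is added so that "this analysis remains sufficiently powered even if one of the other sites under-recruits".

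Section 3.6 defines that analysis. Patients are put into quartiles by week 0 SAQ score, and then the mean, confidence interval and standard deviation of "change scores for change at 'a little better' will be calculated. Analysis of variance will be calculated for the four quartiles". It adds: "Effect size (eta) will be calculated". The rating comes from the global rating of change questionnaire in section 3.3: "The 11-point scale ranges from -5 (a great deal worse) to 5 (A great deal better". Repeated ratings at the same level are averaged so that "each patient can contribute just one value to the population average of the SAQ change score at any level of global change". The MCID itself is built the same way: "any patient who has provided a global rating of change of 'little better' will contribute an initial and final SAQ score".

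Section 3.2 gives a different recruitment figure for the same study: 30 to 50 patients at each of five sites.

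**The concern.** The sample size paragraph treats each recruit as one analysed value. The analysis it serves does not. It compares SAQ change at a single level of an 11-point scale, and a recruit who never reports that level at weeks 4, 8, 12 or 16 is absent from the ANOVA. Four groups of 25 would therefore need 100 contributors, not 100 recruits, and the protocol neither states an expected contributing share nor inflates for it.

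The analysis asks whether one MCID can be applied across the whole range of quality-of-life deficit. Section 3.6 makes the use of the existing MCID method depend on the three checks raising no problems. A reader of section 3.4.3 will believe this check has 70% power at the stated effect size. If the true power is well below that, a non-significant result on its own is weak support for a single MCID.

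**Working it through.** **Inputs.** Four groups, 25 per group, effect size 0.3, alpha 5%, stated power 70% (section 3.4.3). Recruitment: 4 × 25 = 100; with the fifth site 5 × 25 = 125 (section 3.4.3); 5 × 30 = 150 to 5 × 50 = 250 (section 3.2). At most one value per patient at the rating *a little better*, none if it is never given (section 3.6). The share of recruits who ever give it is not in the protocol, so it is varied as an assumption.

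**Formula.** One-way ANOVA with k = 4 equal groups and N patients analysed: power = P(F′ > F crit), where F′ is noncentral F with degrees of freedom 3 and N − 4 and noncentrality λ = N f².

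**Step 1: the plan's own figure.** N = 100, f = 0.3: λ = 100 × 0.09 = 9, df = (3, 96), power 69.2%. This reproduces the stated 70%. Other readings of the effect size do not: eta = 0.3 (f = 0.314) gives 73.7%, eta-squared = 0.3 gives over 99.9%, and a pairwise standardised difference of 0.3 with 25 per group gives 18.4%. Cohen's f is the reading intended.

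**Step 2: contributors needed.** Reaching 70% takes N = 102. With 98 contributors power is 68.1%; with 95 it is 66.6%. At 100 recruits, therefore, about 98 to 100 must give the rating for the statement to hold to within 2 percentage points.

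**Step 3: power when only a share p of R recruits contributes.** N = pR, f = 0.3, equal groups:

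| Share p | R = 100 | R = 125 | R = 150 | R = 250 |
|---|---|---|---|---|
| 100% | 69.2% | 80.0% | 87.5% | 98.6% |
| 95% | 66.6% | 77.6% | 85.5% | 98.1% |
| 90% | 63.8% | 75.0% | 83.3% | 97.4% |
| 80% | 57.9% | 69.2% | 78.1% | 95.5% |
| 70% | 51.4% | 62.4% | 71.6% | 92.4% |
| 50% | 37.0% | 46.1% | 54.7% | 80.0% |
| 40% | 29.4% | 37.0% | 44.4% | 69.2% |
| 30% | 21.9% | 27.5% | 33.2% | 54.7% |

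**Step 4: share needed for 100 contributors.** 100/100 = 100%; 100/125 = 80%; 100/150 = 67%; 100/250 = 40%.

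**Step 5: effect detectable with 70% power.** f = 0.30 with 100 contributors, 0.34 with 80, 0.44 with 50 and 0.58 with 30.

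Quartiles are formed on all patients at week 0, so contributors may be spread unevenly over them. The equal-group figures above do not allow for that.

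**The case against.** The size of the loss rests on an assumed share. Each patient has four visits at which to give the rating, one such rating is enough, and the patients are starting a new biologic, so the 11 levels need not be equally likely. At a 90% or 95% share, 100 recruits still give 64% or 67% power. This stands: the protocol shows that power can fall below 70%, not by how much.

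Recruitment may also exceed 100. Section 3.4.3 itself aims for 125 with the fifth site, and if no site falls short those patients enter the analysis. Section 3.2's 150 to 250 would tolerate shares of 67% down to 40%. This also stands, but it does not repair section 3.4.3, which commits the fifth site to another site's shortfall and does not use the section 3.2 numbers.

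One could argue that the ANOVA uses all change scores, since its sentence does not repeat the restriction. The text does not support that. The preceding sentence restricts the change scores to that rating, and the question posed is whether the MCID, which is defined at that rating, is independent of deficit.

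Finally, section 3.6 sets no p-value rule for what counts as a problem, and it already plans confidence intervals and an effect size. The MCID estimate is also not computed from this test. The consequence is therefore a risk of misreading rather than a faulty decision rule, and how to interpret a non-significant result could properly be left to the SAP. The mismatch itself cannot be left there, because the protocol states the sample size, its justification and the analysis it serves.

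**Conclusion.** The concern holds. The power calculation is correct for 100 analysed values, but it is applied to 100 recruits, whereas the analysis named as its basis takes values only from patients who give one particular rating. At 100 recruits the stated power requires a contributing share of essentially 100%, a conclusion that needs no assumption about the actual share. The illustrative losses (58% power at an 80% share, down to 22% at 30%) do rest on an assumed share, on f = 0.3 and on equal groups. Whether the stated power is met in practice depends on that share and on which recruitment target applies: 100, 125, or 150 to 250. This should be corrected in the protocol; it does not invalidate the study or the MCID estimate.

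**What to change.** In section 3.4.3, state the power for the number of patients expected to give at least one *a little better* rating, over a stated range of shares. For 100 recruits that is about 51% at a 70% share, 37% at 50% and 22% at 30%. Use one reconciled recruitment target in sections 3.2 and 3.4.3.

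As a clarification, add that a non-significant ANOVA alone will not be taken to show that one MCID applies at all severities, and that this judgement will rest on the quartile confidence intervals and effect size already planned in section 3.6.

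The cost is protocol wording and a less favourable stated power at 100 recruits; the restatement needs no extra patients. If about 70% power is to be kept, the recruits needed are about 100 divided by the share: 143 at 70%, 200 at 50% and 250 at 40%, all within the upper limit implied by section 3.2. At a 30% share it would be 100/0.3 = 333, which exceeds that limit.
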